4.2 Secondary Outcome

The secondary outcome of effectiveness will be assessed on a monthly basis. Pharmacists will be instructed to deliver vaccine hesitancy counseling to one to two vaccine-hesitant individuals each week (towards a target of at least 5 per month). Using Qualtrics or a paper survey, pharmacists will document the following on a daily basis: A) how many vaccine-hesitant individuals they provided vaccine hesitancy counseling to; B) of those individuals, how many received a COVID-19 vaccine; C) the self-reported age, race, and gender of the individual who was counseled.

Effectiveness will be calculated as the proportion of counseled individuals who received a vaccine, or B/A. Individuals who are counseled and schedule a vaccine at a later date will not be counted in the numerator (B) until they have actually received a vaccine. Effectiveness scores will range from 0 to 1, with higher scores reflecting a greater percentage of vaccine-hesitant individuals who received a vaccine. During virtual facilitation, trial facilitators will be provided with bi-weekly effectiveness data so they can share the results with the pharmacies to assess performance and identify ways to improve implementation processes and intervention effectiveness.

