Study Phases	
 1. Screening: identifying pharmacies in the RURAL-CP network that meet the eligibility criteria 2. Enrollment by invitation: inviting select pharmacies via email, confirming eligibility of those interested, obtaining verbal informed consent 3. Standard Implementation Period: participants complete one or two 8-week period(s), which involves: completing a 30-minute online training; watching a webinar; implementing the vaccine hesitancy counseling intervention with 10 vaccine hesitant patients per 8-week period; meeting with an SP once per month to have their fidelity to the intervention evaluated 4. Virtual Facilitation Period: participants complete one or two 8-week period(s), which involves: a virtual site visit from a trained virtual facilitator; at least weekly calls with the facilitator; implementing the vaccine hesitancy counseling intervention with 10 vaccine hesitant patients per 8-week period; meeting with an SP once per month to have their fidelity to the intervention evaluated 5. Follow-up: select pharmacies will have one 8-week follow-up period, during which they will continue to implement the vaccine hesitancy counseling intervention with 10 vaccine hesitant patients 6. Qualitative Data Collection: select participants (12 total) will complete a 60-minute interview to assess feasibility and performance of the implementation approaches

Efficacy Evaluations	
Primary outcome: trained study staff will use a fidelity observation guide to rate pharmacists' vaccine hesitancy counseling during recorded counseling sessions. The fidelity measure focuses on the competence of the pharmacist (7 items) in their delivery of the vaccine hesitancy counseling intervention. Each competence item will be assessed on a scale from 0 to 2, with 0 = skill not demonstrated, 1 = skill needs development, and 2 = skill demonstrated with competence.
 
Secondary outcome: using an online survey, pharmacists will document the following on a daily basis:
 
 A) how many vaccine-hesitant individuals they provided vaccine hesitancy counseling to; B) of those individuals, how many received a COVID-19 vaccine; C) the self-reported age, race, and gender of the individual who was counseled. 
Effectiveness will be calculated as the proportion of counseled individuals who received a vaccine, or B/A. Scores will range from 0 to 1.

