3.2 Standard Implementation Period

After pharmacy participants are enrolled, they will then complete one or two 8-week "standard implementation" period(s), depending on the step to which they are randomly assigned. At the beginning of this period, they will be asked to complete a 30-minute online training about COVID-19 vaccine hesitancy counseling and watch a live or pre-recorded webinar (their choice) that provides up-to-date information about COVID-19 vaccinations and boosters. After completion of the training and webinar, participants will be asked to implement the vaccine hesitancy counseling intervention with 10 vaccine hesitant patients per 8-week period. Pharmacists will use Qualtrics or a paper survey to document the extent to which the intervention results in customers getting vaccinated. They will specifically document the number of customers they offered the intervention to, the number who refused, and the number who agreed to be vaccinated. No identifiable customer-level data will be provided by the pharmacies.

Additionally, during the standard implementation period(s), trained study staff will observe and rate counseling fidelity two times per month for each participating pharmacy. We will use a fidelity rating scale to assess fidelity of delivery of the intervention during 4-8 total observed intervention sessions per pharmacy (4 per 8-week period). Since pharmacists have reported difficulties getting patients to agree to be recorded, affecting data collection, we will use standardized patients (SPs) in lieu of real patient conversations. Two SPs will have a total of 8 standardized scripts, each expressing different concerns about the Covid vaccine. The project manager will schedule a 20-minute block with an SP and participating pharmacist and send a Zoom link. Pharmacists will be randomized to script and order of the presentation of two SP scenarios. On the Zoom call, SPs will enact two of their cases, to which the pharmacist will ideally respond with the ASORT intervention. The encounter will be recorded using the secure Express Dictate mobile or desktop app and later rated for counseling fidelity. SPs will meet with each pharmacist one time per month, portraying different personas each time.

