To increase the likelihood that each participating pharmacy submits the requested study data, a fax will be sent to each participating pharmacy that is missing data after the first month of standard implementation to remind them of what is needed. This fax may be sent every 2 weeks as needed to acquire missing study data, with a follow-up phone call a week after the fax to non-responders.

At the end of the standard implementation period(s), participating pharmacy staff (up to 5 per pharmacy) will complete Qualtrics surveys to assess implementation outcomes (feasibility, acceptability, appropriateness).

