3.3 Virtual Facilitation Period

After the implementation outcome surveys have been completed, pharmacies will "crossover" to the virtual facilitation period(s). This period will begin with a virtual site visit from a trained virtual facilitator and be followed by at least weekly calls with a local champion (a participating pharmacist) and at least bi-weekly calls with each participating pharmacist to provide feedback on intervention fidelity (from observations of interventions delivered). The virtual site visit over Zoom will establish the personnel and workflows at each pharmacy and allow the facilitator to establish rapport. Weekly Zoom calls will allow the virtual facilitator to work with a site champion to review overall implementation challenges associated with approaching patients, delivering the intervention, and documenting results. Lastly, either the facilitator or the local champion can request and schedule a Zoom call to go over any pressing implementation issue in need of rapid attention (e.g., technical difficulties with the website).

During each 8-week virtual facilitation period (one or two periods, depending on the step to which pharmacies are randomly assigned), pharmacists will again be asked to implement the intervention with 10 vaccine hesitant patients. Like during the standard implementation period, pharmacists will use Qualtrics or a paper survey to document the extent to which the intervention results in customers getting vaccinated. Similarly, fidelity observations (4-8 total per pharmacy) will be collected using the same processes described in Section 3.2. Additionally, at the end of virtual facilitation period(s) participating pharmacy staff (up to 5 per pharmacy) will again be asked to complete Qualtrics surveys to assess implementation outcomes (feasibility, acceptability, appropriateness).

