3.4 Follow-up

Pharmacies randomized to blocks 1-4 will have one 8-week follow-up period. During this period, pharmacists will continue to use Qualtrics or a paper survey to document the extent to which the intervention results in customers getting vaccinated. They will specifically document the number of customers they offered the intervention to, the number who refused, and the number who agreed to be vaccinated.

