4.3 Other Measures

Acceptability, appropriateness, and feasibility of the vaccine hesitancy intervention and implementation approaches (standard, facilitation) will be measured using validated surveys³³. Each

measure includes 4 items (e.g., “intervention X seems doable” [feasibility]) measured on a 5-point response scale that ranges from “strongly disagree” (coded as 1) to “strongly agree” (coded as 5). For each pharmacy, we will average scores across the pharmacy staff members who complete the surveys.

Uptake will be calculated as the number of times vaccine hesitancy counseling was offered divided by the number of individuals who expressed vaccine hesitancy when offered the vaccine.

Sustainment will be assessed by the continued measurement of fidelity, effectiveness, and uptake during the “follow-up” periods.

*Organizational structure and context measures*³⁴: one pharmacist per pharmacy will complete the Organizational Structure survey^{35,36}, which measures: location, type (e.g., independent, chain), setting (e.g., retail, specialty), size (weekly prescriptions, staffing), technological capacity (dispensing system), and services provided. The Organizational Context measure (completed by 5 pharmacy staff members) assesses CFIR inner setting constructs³⁴ that reflect organizational culture/capacity for change³⁷, learning climate, leadership, and resources^{38,39}. All items are measured on a 5-point agree-disagree response scale, with higher scores reflecting a stronger implementation context. For each pharmacy, we will average scores across the five pharmacy staff members who complete the surveys.

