5.2 Secondary Outcome

For the secondary outcome of effectiveness, we will use generalized linear mixed models (GLMM) to investigate whether pharmacies are more effective at addressing vaccine hesitancy during virtual facilitation when compared to standard implementation. The effectiveness outcome will be binary (vaccine-hesitant patient accepts vaccine after counseling = 1; vaccine-hesitant patient does not accept vaccine after counseling = 0). We will report the odds ratio estimate of accepting the vaccine after counseling for the virtual facilitation approach (facilitation versus standard) along with a 95%

confidence interval. The model-building approach for our secondary effectiveness outcome will follow four analysis steps: 1) an unadjusted before/after of the effect of the virtual facilitation approach (ignoring period/time effect); 2) the inclusion of time period (i.e., steps) to examine if any potential intervention effect relates only to the intervention or also to an independent effect of calendar time; 3) an adjustment for patient's age, race, and gender and potential pharmacy-level confounders, such as pharmacy size; 4) the possible interaction between time period and intervention. The impact of virtual facilitation on effectiveness could potentially change over time if vaccine acceptance rates increase with time and as pharmacists gain experience with counseling vaccine-hesitant patients. We aim to explore this question through the inclusion of an interaction between period/time and intervention effect in Model 4. Additionally, the intraclass correlation coefficients (ICC) will be estimated and reported, so this information will be available for power analyses for future investigations using similar designs and outcomes. In order to reduce potential bias, during the virtual facilitation period, pharmacists will be instructed to approach patients that they did not approach during the standard facilitation period, which is feasible given the large number of unvaccinated individuals in the communities in which RURAL-CP pharmacies are located.

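### The secondary outcome is recorded as agreed (3.2, 3.4), coded as accepts (5.2) and defined as received (4.2), and aggregate records (8.2) do not fit the patient-level adjustment in 5.2.

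*Combined protocol and SAP*

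**What the plan says.** **Received.** The synopsis and 4.2 take the number counselled (A) and "of those individuals, how many received a COVID-19 vaccine" (B), and score B/A. Section 4.2 adds that people who "schedule a vaccine at a later date will not be counted in the numerator (B) until they have actually received a vaccine". Section 8.2 says the number who received a vaccine goes to the study team, and Table 1 describes the outcome as the proportion who vaccinate after counselling.

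**Agreed.** Section 3.2 lists as specific items the number offered the intervention, "the number who refused, and the number who agreed to be vaccinated". Section 3.4 repeats this for follow-up: "the number of customers they offered the intervention to, the number who refused, and the number who agreed to be vaccinated". Sections 3.2, 3.3 and 3.4 also say in general terms that the survey documents how far the intervention leads to customers being vaccinated. Section 3.3 does not repeat the itemised list.

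**Accepts.** Section 5.2 codes "vaccine-hesitant patient accepts vaccine after counseling = 1", and 5.3 states its 5% and 15% as proportions accepting.

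**Form of the record.** Section 4.2 item C collects age, race and gender of the person counselled, and 5.2 step 3 adjusts for them. Section 8.2 says fidelity and effectiveness data are recorded in aggregate, without identifying or personal health information. Section 3.2 likewise rules out identifiable customer-level data.

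**Follow-up.** Section 4.3 states: "Sustainment will be assessed by the continued measurement of fidelity, effectiveness, and uptake".

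**The concern.** Agreeing and receiving are different events, and 4.2 itself separates them by excluding people who have only scheduled. If the survey were built from the item list in 3.2 and 3.4, it would capture a different numerator from the one 4.2 defines. The denominator would differ too, since offered is not counselled. The same wording in 3.4 affects the sustainment measure, which relies on effectiveness still being measured in follow-up.

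The second problem is linkage. Adjusting for patient age, race and gender requires knowing, for each counselled person, both those items and whether a vaccine was received. If only totals per pharmacy and period are kept, step 3 of 5.2 cannot be fitted as described. A link that is not recorded at source cannot be recovered at analysis.

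A lesser gap is that no section sets a common time window for counting a later vaccination, or says how it is carried back to the counselling entry.

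**Working it through.** **1. One person under each section.** Take someone who is counselled, agrees, schedules, and is not vaccinated.

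| Section | Wording | Result |
|---|---|---|
| 3.2, 3.4 | agreed | success |
| 5.2 | accepts | arguably success |
| Synopsis, 4.2, 8.2, Table 1 | received / vaccinate | failure (stays in A, not in B) |

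**2. What each analysis needs.**
- B/A in 4.2: two counts.
- 5.2 steps 1 and 2 (condition, then period): counts per pharmacy and period suffice, because no patient-level covariate enters.
- 5.2 step 3: receipt linked to age, race and gender for each person, or an equivalent full cross-tabulation. A total of receipts plus separate totals by gender does not show who was vaccinated. No section states the link.

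**3. Size of agreed versus received.** The documents give no conversion share, so c, the share of those who agree who are then vaccinated, is assumed equal in both conditions. Taking the 5% and 15% of 5.3 as received rates, the recorded agreed rates are 0.05/c and 0.15/c.

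| c | Agreed rates | Difference | Odds ratio |
|---|---|---|---|
| 100% | 5.0% vs 15.0% | 10.0 points | 3.35 |
| 90% | 5.6% vs 16.7% | 11.1 points | 3.40 |
| 80% | 6.3% vs 18.8% | 12.5 points | 3.46 |
| 70% | 7.1% vs 21.4% | 14.3 points | 3.55 |

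With no true effect and equal c, the difference stays zero.

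**4. Size of late receipt.** Figure 1 has 16 analysed block-periods (8 standard, 8 facilitation). With 5 pharmacies per block and 10 patients per period (5.3), 16 × 5 × 10 = 800, which reproduces the plan's sample size. Expected cell rates were put through generalised least squares with an exchangeable ICC of 0.05 (5.3) and variance 0.10 × 0.90 = 0.09. The standard error is 0.0405 with six period effects and 0.0212 without.

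Let d be the assumed share of vaccinations falling after the 8-week period of counselling. The true difference is 10 points.

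| How late receipts are handled | Period-adjusted, d = 5% / 10% | Unadjusted, d = 5% / 10% |
|---|---|---|
| Credited to counselling; follow-up in blocks 1 and 4 records receipt | 10.0 / 10.0 | 9.6 / 9.2 |
| Credited to counselling; follow-up does not record receipt | 9.6 / 9.3 | 9.4 / 8.8 |
| Counted in the period of receipt | 9.4 / 8.8 | 9.8 / 9.6 |
| Logged only under facilitation | 10.25 / 10.5 | 10.25 / 10.5 |

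The largest period-adjusted shift is 10.0 − 8.8 = 1.2 points, about 0.3 of the 4.0-point standard error. With no true effect and a 5% rate in both conditions, the last row gives +0.25 / +0.5 points.

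**The case against.** The strongest reply is that receipt is already planned. Section 4.2, the defining section, puts A, B and C on the same Qualtrics or paper survey. Section 8.2 sends the number who received a vaccine to the team, and 3.2 to 3.4 describe the survey's purpose as documenting vaccination. Nothing says the list in 3.2 and 3.4 is exhaustive; it may serve the uptake measure in 4.3, which uses counselling offers. This stands. A reader might infer that receipt is not collected and the planned endpoint cannot be built, and the documents do not support that.

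Second, the aggregate wording may be loose. The same sentence covers fidelity, which is rated session by session. Pharmacists counsel one or two people a week and document daily, so many daily entries would concern one person, with receipt beside age, race and gender. This shows that step 3 may be feasible in practice. It does not supply a stated link, and it leaves 8.2 in conflict with 5.2.

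Third, a reader might infer that late vaccinations materially bias the comparison, perhaps in favour of facilitation. Only in that condition do weekly calls cover "approaching patients, delivering the intervention, and documenting results", and only there do facilitators share effectiveness data with pharmacies. In the standard period, 3.2 provides reminders: "This fax may be sent every 2 weeks as needed to acquire missing study data". Those are not described as asking for late receipts, but no section says that late receipts go unlogged there. The shares in the calculation are assumed and the resulting shifts are small, so this inference is not established.

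**Conclusion.** The sections conflict on what counts as a success, and 8.2 as worded does not fit step 3 of 5.2. Both conflicts are on the page and need no assumption. What they would do to the result is not known: the documents give neither a conversion share from agreement to vaccination nor a distribution of delay.

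Under the assumed values, recording agreement instead of receipt would report a true 10-point difference as 11.1 to 14.3 points (c from 90% to 70%, equal in both conditions). Late receipt at d = 5–10% would move the period-adjusted estimate by 0 to 1.2 points. The direction depends on how late receipts are captured, and the shift is small against the standard error. Severity therefore rests on the definition and record conflict alone. It is low to moderate and confined to the secondary outcome and its follow-up measurement; the primary fidelity outcome is untouched.

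**What to change.** - **One outcome.** Use receipt of a COVID-19 vaccine in 3.2, 3.4 and 5.2, to match 4.2. Offered and agreed may stay as extra items. State in 5.3 whether the 5% and 15% are receipt rates.
- **One record.** Keep one de-identified row per counselled person: condition, period, age, race, gender, received yes/no. Fit the 5.2 GLMM to those rows.
- **Confidentiality wording.** Replace the aggregate phrase in 8.2, and square the row with the limits on customer data in 3.2 and 8.2, for example by holding period instead of date and age in bands.
- **Late vaccinations (secondary clarification).** Credit a later vaccination to the condition at counselling, and use the same ascertainment window in all periods.

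The cost is a change to the Qualtrics and paper forms and one look-up per counselled person when the window closes. No extra patients are needed. In blocks 2, 3, 5 and 6 (4 × 5 = 20 of 30 pharmacies) no follow-up period comes directly after facilitation, so covering a window there would need a short data-collection tail. That tail is optional: with late receipts credited to counselling and recorded in the follow-up of blocks 1 and 4, the period-adjusted estimate is 10.0 without it.

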4.3 Other Measures

Acceptability, appropriateness, and feasibility of the vaccine hesitancy intervention and implementation approaches (standard, facilitation) will be measured using validated surveys³³. Each

measure includes 4 items (e.g., “intervention X seems doable” [feasibility]) measured on a 5-point response scale that ranges from “strongly disagree” (coded as 1) to “strongly agree” (coded as 5). For each pharmacy, we will average scores across the pharmacy staff members who complete the surveys.

Uptake will be calculated as the number of times vaccine hesitancy counseling was offered divided by the number of individuals who expressed vaccine hesitancy when offered the vaccine.

Sustainment will be assessed by the continued measurement of fidelity, effectiveness, and uptake during the “follow-up” periods.

*Organizational structure and context measures*³⁴: one pharmacist per pharmacy will complete the Organizational Structure survey^{35,36}, which measures: location, type (e.g., independent, chain), setting (e.g., retail, specialty), size (weekly prescriptions, staffing), technological capacity (dispensing system), and services provided. The Organizational Context measure (completed by 5 pharmacy staff members) assesses CFIR inner setting constructs³⁴ that reflect organizational culture/capacity for change³⁷, learning climate, leadership, and resources^{38,39}. All items are measured on a 5-point agree-disagree response scale, with higher scores reflecting a stronger implementation context. For each pharmacy, we will average scores across the five pharmacy staff members who complete the surveys.

5 STATISTICAL CONSIDERATIONS

We will use the principles of intention-to-treat, using multiple imputations if needed for missingness, for all statistical analyses related to primary and secondary endpoints. Descriptive statistics will be computed for all quantitative implementation outcomes in Table 1.

5.1 Primary Outcome

The primary outcome of fidelity is captured at the pharmacy level. For our primary analysis of the fidelity outcome, we will use linear mixed-effects models (LMM) to compare the level of fidelity between the two implementation approaches (standard approach vs. virtual facilitation). We will report point estimates for the group mean difference along with a 95% confidence interval. The model-building approach will follow four analyses steps: 1) an unadjusted before/after of the effect of the virtual facilitation approach (ignoring period/time effect); 2) the time period (i.e., steps/blocks) to examine if any potential intervention effect relates only to the intervention or also to an independent effect of calendar time; 3) an adjustment for potential pharmacy-level confounders, such as size and learning climate; and 4) the interaction between period and intervention effect.

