4 STUDY EVALUATIONS AND MEASUREMENTS

4.1 Primary Outcome

Our primary outcome is fidelity to the vaccine hesitancy counseling intervention, assessed at the pharmacy level. Our fidelity measure is based on a theoretical framework of fidelity measurement³⁰ as well as a validated fidelity checklist³¹. The fidelity measure focuses on the competence of the pharmacist (7 items) in their delivery of the vaccine hesitancy counseling intervention.

The competence items focus on the skillfulness of intervention delivery: expressed empathy; used a non-confrontational manner; spoke confidently without using jargon; emphasized patient autonomy; reflected back patient's statements accurately; used a respectful demeanor, and used evidence-based responses when responding to patient vaccine concerns. Each competence item will be assessed on a scale from 0 to 2, with 0 = skill not demonstrated, 1 = skill needs development, and 2 = skill demonstrated with competence. Competence scale scores will range from 0 to 14, with higher scores reflecting greater competency in the delivery of ASORT. Fidelity will be measured for each pharmacist approximately twice per month under the standard implementation approach and approximately twice per month under the virtual facilitation approach. In pharmacies with more than one pharmacist, fidelity ratings will be averaged to achieve a pharmacy-level measure.

Trained staff will rate fidelity after reaching 80% inter-rater reliability during training³². Staff who are blinded to the pharmacist's group assignment will use a fidelity observation guide to rate pharmacists' vaccine hesitancy counseling during recorded counseling sessions. During virtual facilitation, ratings will be shared with the facilitators who provide feedback and coaching to pharmacists towards improving fidelity.

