5.3 Power Analyses

For the primary outcome of fidelity, captured at the pharmacy level, we wish to compare the fidelity scores under standard implementation versus fidelity scores under virtual facilitation. We expect each pharmacy to have approximately 4 fidelity assessments per time period (i.e., a period of 8 weeks). A sample of 30 pharmacies in an incomplete stepped-wedge cluster-randomized design with six periods (five steps), and an average of 10 fidelity assessments per pharmacy yields a total sample size of 320 assessments, which achieves over 90% power to detect a difference between means of 0.53 with a standard deviation of 1 (i.e., moderate effect size). The test statistic is based on a two-sided Wald Z-test with $ICC = 0.6$ and $\alpha = 0.05$. Given that we will have repeated fidelity measures from the same pharmacists over time, we have specified a conservative ICC (which in a stepped wedge design does not impact power calculations significantly).

For the secondary outcome of effectiveness, we expect each pharmacy to identify approximately 10 vaccine-hesitant patients during each time period (i.e., a period of 8 weeks). A sample of 30 pharmacies in an incomplete stepped-wedge cluster-randomized design with six periods (five steps) and an average of 27 patients per pharmacy yields a total sample size of 800 patients, which achieves over 90% power to detect a difference between effectiveness proportions of 10%. The proportion of vaccine-hesitant patients accepting the vaccine during the virtual facilitation approach is assumed to be 15% compared to 5% under the standard implementation period. These estimates are based on a review of reported changes in vaccine acceptance for evidence-based vaccine hesitancy interventions⁴⁰. The test statistic is based on a two-sided Wald Z-test with $ICC = 0.05$ and $\alpha = 0.05$. We note that the actual sample size should exceed 800 patients since we expect pharmacies will continue to identify vaccine-hesitant individuals during the follow-up periods.

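### The primary mixed model has no stated correlation structure or unit of analysis, and its power figure rests on a single ICC of 0.6 that is favourable, not conservative

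*Combined protocol and SAP*

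**What the plan says.** Section 5.1 (Primary Outcome) says "we will use linear mixed-effects models (LMM) to compare the level of fidelity between the two implementation approaches". It lists four model-building steps, with period added at step 2. It names no random effect, covariance structure, robust variance or small-sample correction.

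Section 5.3 (Power Analyses) describes "A sample of 30 pharmacies in an incomplete stepped-wedge cluster-randomized design with six periods (five steps"), about 4 ratings per pharmacy per 8-week period and 320 ratings in total, "which achieves over 90% power to detect a difference between means of 0.53 with a standard deviation of 1". The test is a two-sided Wald Z-test at alpha 0.05 with ICC 0.6. That is the only correlation given for the primary outcome; effectiveness has its own ICC of 0.05. The plan adds: "we have specified a conservative ICC (which in a stepped wedge design does not impact power calculations significantly").

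On how the ratings arise, section 3.2 has one call per pharmacist per month and says "On the Zoom call, SPs will enact two of their cases". The four ratings in a period therefore come from two calls. On the unit, sections 4.1, 5.1 and 5.3 all place the outcome at pharmacy level. The only averaging described is across pharmacists, where "fidelity ratings will be averaged to achieve a pharmacy-level measure", and section 2.3 expects one pharmacist per pharmacy.

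**The concern.** A single ICC makes every pair of ratings from one pharmacy equally correlated, whether they are minutes apart on one call or months apart. Two features of the design make that doubtful. Paired scenarios share a call and a day. Pharmacies may also learn at different rates, which common period effects cannot remove; section 5.2 itself expects pharmacists to gain experience over time.

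Condition changes only from one pharmacy-period to the next. Variance at that level therefore feeds directly into the error of the facilitation effect. If the fitted model leaves it out, the confidence interval for the primary comparison may be too narrow. If the power calculation leaves it out, the trial may be less sensitive than stated. A reader who accepts that the ICC hardly matters would not look for either problem.

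**Working it through.** **Inputs.** From section 5.3: difference 0.53, SD 1 (read as total SD), ICC 0.6, 4 ratings per pharmacy-period, two-sided alpha 0.05. From Figure 1: 16 standard or facilitation block-periods × 5 pharmacies = 80 pharmacy-periods; 80 × 4 = 320 ratings, which matches the plan with follow-up excluded. Assumed, because the documents give neither: the CAC, and the share *c* of total variance that is common to one call.

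**Formula.** Put pharmacy variance a = ICC × CAC, pharmacy-by-period variance b = ICC × (1 − CAC), and residual e = 1 − ICC − c. A mean of four ratings from two calls has within-pharmacy variance w = b + c/2 + e/4. Figure 1 has three sequences (standard-facilitation, standard-standard-facilitation, standard-facilitation-facilitation), each with 10 pharmacies over the two seasons. With a fixed effect for every period, generalised least squares gives

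Var = 3w(2a + w)(3a + w) / [5(3a + 2w)(5a + 2w)], and power = Φ(0.53/SE − 1.96).

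**The plan's own figure.** CAC 1 and c = 0 give a = 0.6 and w = 0.4/4 = 0.1. Var = 3(0.1)(1.3)(1.9)/[5(2.0)(3.2)] = 0.741/32 = 0.02316. SE = 0.1522, and power = Φ(3.483 − 1.960) = 93.6%. The stated figure reproduces. Reading SD 1 as the residual SD gives 59.6% and does not.

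**Adding pharmacy-by-period variance (ICC 0.6, c = 0).** For example, at CAC 0.9: a = 0.54, w = 0.06 + 0.1 = 0.16, Var = 3(0.16)(1.24)(1.78)/[5(1.94)(3.02)] = 0.03617.

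| CAC | a | w | SE | Power | Difference with 90% power, (1.960 + 1.282) × SE |
|---|---|---|---|---|---|
| 1 | 0.60 | 0.10 | 0.152 | 93.6% | 0.49 |
| 0.95 | 0.57 | 0.13 | 0.172 | 86.7% | 0.56 |
| 0.9 | 0.54 | 0.16 | 0.190 | 79.6% | 0.62 |
| 0.8 | 0.48 | 0.22 | 0.220 | 67.3% | 0.71 |

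Power falls below 90% once the CAC is under about 0.973. With CAC 1, a call share of 0.05 gives 90.8% and 0.10 gives 87.9%; the 90% point is 0.064. CAC 0.9 with a call share of 0.1 gives 74.0%.

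**Varying only the ICC (CAC 1, c = 0).** This needs nothing from outside the plan. With total SD fixed at 1, a lower ICC leaves more variance within pharmacies, where the comparison is mostly made.

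| ICC | w | SE | Power |
|---|---|---|---|
| 0.6 | 0.100 | 0.152 | 93.6% |
| 0.5 | 0.125 | 0.169 | 88.1% |
| 0.4 | 0.150 | 0.183 | 82.6% |
| 0.2 | 0.200 | 0.203 | 74.3% |

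An ICC of at least 0.534 is needed for 90% power. Power is insensitive to the ICC only at low values: it is also 74.3% at ICC 0.05.

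**Type I error, nominal 5%.** Null trials were simulated on the Figure 1 layout (2,000 to 6,000 per setting), with period effects and a REML fit with a pharmacy intercept only.

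- Individual ratings, no extra variance: 4.6% and 5.0% in separate runs.
- Individual ratings, CAC 0.9: 9.4% to 10.4%. CAC 0.8: 13.3% to about 16%.
- Individual ratings, CAC 1, call share 0.1: 7.6% and 8.4%.
- Pharmacy-period means, CAC 0.8 to 0.9, with or without a call effect: 4.8% to 6.1%.

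**The case against.** The strongest reply is that section 5.1 does not commit to a pharmacy intercept on individual ratings. An ICC used for planning is not an analysis model, and three sections call the outcome pharmacy-level. If the model is fitted to pharmacy-period means, type I error stays at about 5-6% even with an intercept only. This stands. A reader might infer that the primary test is anti-conservative as planned, but the documents do not support that. Inflation needs individual ratings, an intercept only and real extra variance, all at once. Against it, section 5.3 counts 320 ratings and nothing averages them within a period, so the rating-level fit is a live reading.

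A reader might also infer that the power figure is wrong. It is not: it follows from its own inputs, and every lower CAC here is an assumption. However, analysing means does not remove the power loss. With equal cells, the means and a correctly specified rating-level model give the same variance.

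Nor do the documents show the same problem for the effectiveness GLMM. Its ICC is 0.05, and a rough linear approximation with 10 patients per period gives type I error of only 5.6% at CAC 0.9 and 6.7% at 0.8. Finally, nothing here argues against averaging across pharmacists as section 4.1 defines.

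**Conclusion.** The concern holds as a specification gap, together with one incorrect statement.

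- **Analysis (conditional).** The unit and correlation structure of the primary model are open. One plausible reading gives type I error of about 10% at CAC 0.9, 13-16% at CAC 0.8, or about 8% with a call share of 0.1. The other reading holds about 5-6%.
- **Power (conditional).** The claim of over 90% holds only for a CAC near 1 and a small call effect. It is about 87%, 80% and 67% at CAC 0.95, 0.9 and 0.8.
- **ICC statement (unconditional within the plan's period-adjusted single-ICC model).** An ICC of 0.6 is the favourable direction. Moving to 0.4 or 0.2 costs 11 or 19 percentage points of power.

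Confidence is moderate, because no CAC or call correlation is given and section 5.1 does not settle the unit of analysis.

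**What to change.** In section 5.1, name one primary model, with fixed effects for calendar period and condition, as either:

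- a rating-level LMM with random effects for pharmacy and pharmacy-by-period, plus Zoom call if it can be estimated; or
- an LMM on pharmacy-period means with a pharmacy intercept. This is simpler, and with two or three scored periods per pharmacy it may be more stable.

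Use a small-sample t reference (Kenward-Roger or similar) in either case.

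In section 5.3, delete the sentence calling the ICC conservative and restate primary power over a grid. On the plan's other inputs, with a z reference and no call effect:

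| ICC | CAC 1 | 0.95 | 0.9 | 0.8 |
|---|---|---|---|---|
| 0.6 | 93.6% | 86.7% | 79.6% | 67.3% |
| 0.4 | 82.6% | 78.2% | 74.1% | 66.9% |
| 0.2 | 74.3% | 72.7% | 71.2% | 68.4% |

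The cost is SAP wording, somewhat wider intervals and a less favourable stated power. A t reference alone (22 to 29 df) takes 93.6% to 91.4-91.9%. If there is no period-level variation, the model with a pharmacy-by-period effect is slightly conservative (3.8% type I error in simulation).
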